### 3 **Section A: Experimental Design**

4 This study will employ a quasi-experimental design utilizing repeated measures (specific  
5 aim 1), followed by cross-sectional analysis (specific aims 2 and 3). The target sample size for  
6 the study will be 25 physical therapists and 90 patients. Patient-reported outcome measures were  
7 selected based upon their reliability, validity and internationally accepted use. Given that there is  
8 no single universal patient reported outcome measure for the shoulder, multiple measures will be  
9 utilized during the third aim of this project.

#### 10 Specific Aim 1

11 The first specific aim will be to determine the reliability of the shoulder symptom  
12 irritability classification scale. To address this aim, the project will analyze paired rater  
13 judgments of shoulder symptom irritability (high, moderate or low) from 90 patients with  
14 shoulder pain. Raters will be physical therapists from multiple clinics trained in rating shoulder  
15 symptom irritability. Prevalence-adjusted, bias-adjusted Kappa for ordinal scales (PABAK-OS)  
16 will be the primary measure of reliability. However, analysis may be adjusted based on the data  
17 distribution.

#### 18 Specific Aim 2

19 The second aim is to compare level of functional limitation between shoulder symptom  
20 irritability groups. To address this aim, the project will analyze patient-reported functional  
21 measures using analysis of variance with post-hoc analysis to compare functional disability  
22 across different levels of shoulder symptom irritability. The independent variable will be the  
23 shoulder symptom irritability level, and dependent variables will include patient-reported  
24 functional status measures. The hypothesis is that patients with higher irritability will report  
25 greater functional deficits.

#### 26 Specific Aim 3

27 The final specific aim is to determine if the level of shoulder symptom irritability dictates  
28 the chosen intervention intensity. To address this aim, raters will select planned intervention  
29 choices for each of the 90 patients, utilizing a pre-specified list of possible physical therapy  
30 interventions. Data analysis will include PABAK-OS for correlation, and independent t-test for  
31 differences between clinical specialist and non-specialist groups. The hypothesis is that patients  
32 with high irritability will be prescribed interventions aimed at minimizing the physical stress to  
33 the affected tissue(s), while patients with low irritability will be prescribed interventions at a  
34 higher intensity to address the physical impairments.

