#### 143 Procedures

144 At least 2 raters will be recruited from each site. Raters will be trained with the following  
145 materials: (1) Collaborative Institutional Training Initiative (CITI) training for those involved in  
146 consenting the patients; (2) the reading of the Staged Approach for Rehabilitation Classification:  
147 Shoulder Disorders with direction to pay special attention to the section on Level 3  
148 classification and Table 3;6(pp 795-6) and (3) a short online narrated presentation to reinforce  
149 understanding of the content. The intent of this training method is to increase the generalizability  
150 of the study results, and to avoid overly specialized training methods that would be difficult to  
151 reproduce clinically.

152        Patients will be recruited by the raters from their regular caseload (Appendix C). Patients  
153 will receive a brief explanation about the study, provide informed consent, and be asked to  
154 complete the functional questionnaires as part of the outpatient admissions process. The first  
155 therapist will rate the patient's shoulder symptom irritability level during the normal examination  
156 process utilizing the intake (Appendix C). Raters will inquire on the presence of night or resting  
157 pain and complete a physical examination including measurement of active and passive shoulder  
158 flexion. Range of motion measurements will be utilized for direct comparison and to determine  
159 the onset of pain during passive motion. Shoulder flexion will be measured utilizing goniometric  
160 procedures described elsewhere. Active range of motion testing will be performed in  
161 standing and passive range of motion testing will be performed in supine.

162        After the first rater has completed their examination and prior to any intervention that  
163 may change the shoulder symptom irritability, a second rater, blinded from the first rater's  
164 assessment, will then examine and rate the subject (Appendix C). In addition to the shoulder  
165 symptom irritability rating, both raters will also be asked to provide a treatment intensity  
166 recommendation based upon the examination findings (Appendix C). Data collection forms will  
167 be placed in a sealed envelope and sent via interoffice mail for analysis. To maintain rater  
168 blinding, raters will be asked to not discuss ratings until data collection is complete.

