#### 172 ***Section D: Statistical Analysis***

173        Descriptive statistics will be used to characterize both raters and patients. Frequencies  
174 will be utilized for categorical variables, and means with standard deviations for continuous  
175 variables.

176        A repeated measures design, utilizing two raters per subject, will be utilized to determine  
177 inter-rater reliability. The raters will independently rate the subject's shoulder symptom  
178 irritability level utilizing the recently developed shoulder symptom irritability scale. The inter-  
179 rater reliability will be evaluated using the PABAK-OS statistic. For evaluation of statistical  
180 significance, a two-tailed confidence interval will be utilized with  $\alpha$  set to 0.05, and the null  
181 hypothesis will be that the PABAK-OS will be  $<0.40$ .

182        Analysis of variance with post-hoc analysis will be utilized for evaluation of differences  
183 in patient reported functional limitation and pain subscales between shoulder symptom  
184 irritability groups. For evaluation of statistical significance,  $\alpha$  will be set to 0.05.

185        Lastly, to evaluate correlation between intervention intensity and diagnosed level of  
186 shoulder symptom irritability, the PABAK-OS statistic will be used. Additionally, independent t-  
187 tests will be utilized to evaluate for difference between groups for hypotheses 1 and 2 of aim 3.  
188 For evaluation of statistical significance,  $\alpha$  will be set to 0.05.

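### The Aim 3 specialist versus non-specialist t-test has no named outcome and leaves out irritability; if run on chosen intensity it does not measure matching and is open to case-mix confounding

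*Combined protocol and SAP*

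**What the plan says.** Section A, Specific Aim 3, sets the question: "The final specific aim is to determine if the level of shoulder symptom irritability dictates" the intensity of the intervention chosen. The hypothesis given there is directional. Patients "with high irritability will be prescribed interventions aimed at minimizing the physical stress to" the tissue, and patients with low irritability receive more intense treatment. Two analyses are named: PABAK-OS for the relation between irritability and intensity, and an independent t-test for "differences between clinical specialist and non-specialist groups".

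Section D repeats this. For the relation between intensity and "shoulder symptom irritability, the PABAK-OS statistic will be used". It then says that independent t-"tests will be utilized to evaluate for difference between groups for hypotheses 1 and 2 of aim 3", and that alpha "will be set to 0.05". The text available contains one unnumbered Aim 3 hypothesis, and it does not mention specialists. Neither section names the dependent variable of the t-test, and neither adjusts for, stratifies by or interacts with irritability. PABAK-OS is not said to be compared between rater groups.

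On how patients reach raters, Section C, Procedures, says: "Patients will be recruited by the raters from their regular caseload". A second, blinded rater then examines the same patient, and both raters recommend a treatment intensity. Each site needs at least two raters, but nothing is said about pairing a specialist with a non-specialist. Sections B.1 and E restrict Aim 3 to patients on whom both raters agree.

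**The concern.** Aim 3 is a question about matching: does intensity follow irritability? A comparison of mean intensity between two groups of raters is a different question. One group may match every patient and another may always choose the middle option, yet with as many high- as low-irritability patients their means are equal. Conversely, if specialists' caseloads are more irritable, the plan's own hypothesis predicts lower mean intensity among specialists even when both groups decide in the same way.

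A null result could therefore hide much closer matching by specialists, and a significant result could reflect patient mix. Either could be misread as evidence about specialist decision-making. Defining who counts as a specialist, or settling the unit of analysis, would not cure this.

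**Working it through.** **The plan's own figure.** There is none for this test: no effect size, standard deviation or power is given. The only sample-size figure, 48 patients, is for the Aim 1 kappa. It is reproduced by the Donner-Eliasziw formula (kappa 0.80 against 0.40, 80% power, two-sided 0.05) at an assumed prevalence of 0.30: 47.6, rounded up to 48. It says nothing about the t-test.

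**Inputs from the documents.**
- 25 raters and 90 patients (Section A).
- 18 specialists among over 80 therapists (Section E). 25 × 18/80 = 5.6, so 6 specialists and 19 others if recruitment is proportional.
- Two raters per patient, both choosing an intensity (Section C).
- Three ordered intensity options, one to be selected (Appendix C).

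**Assumptions.**
- Intensity is scored 1 (least stress) to 3, and the test is two-sided at 0.05.
- A rater picks the level the hypothesis expects with probability *a*, and otherwise picks one of the three levels at random. The exact-match share is then *a* + (1 − *a*)/3: 93% for *a* = 0.9, 87% for 0.8 and 60% for 0.4.
- The number of agreed patients is not stated. 60 is used beside the maximum of 90.

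**Step 1: better matching, same patients.** If *m* is the mean expected level, mean chosen intensity = *a·m* + (1 − *a*) × 2.
- Irritability in thirds: *m* = 2, so the mean is 2 for every *a*. With 90% versus 40% matching the true difference is 0. In simulation the intensity t-test rejects about 5-6%, while a t-test on mismatch (distance between chosen and expected level) rejects well over 90% with 60 to 90 patients.
- High/moderate/low 50/30/20: *m* = 0.5 × 1 + 0.3 × 2 + 0.2 × 3 = 1.7. Specialists average 0.9 × 1.7 + 0.1 × 2 = 1.73 and others 0.4 × 1.7 + 0.6 × 2 = 1.88, a difference of −0.15. The intensity t-test rejects about 13-19%. The sign and size of that difference come from the skew of the mix, so it would be read as lower intensity, not closer matching.

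**Step 2: equal matching, different caseloads.** Take *a* = 0.8 in both groups and thirds for non-specialists. Give specialists' caseloads *s* more high- and *s* fewer low-irritability patients. Their *m* falls by 2*s*, so intensity differs by 0.8 × 2*s* = 1.6*s* if each group rates only its own patients.

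The second rater dilutes this. With random pairing of 6 and 19 raters, the share of ratings made on specialist-caseload patients is 0.5 × (1 + 5/24) = 0.604 for specialists and 0.5 × 6/24 = 0.125 for others. The shift is multiplied by 0.604 − 0.125 = 0.479, so 10/15/20 points become about 4.8/7.2/9.6 points.

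False rejection of the intensity t-test:

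| Pairing | 10 points | 15 points | 20 points |
|---|---|---|---|
| Random, 90 patients | 8% | 12% | 18% |
| Random, 60 agreed patients | 7% | 10% | 13% |
| Both raters of the same type, 90 patients | 25% | 40% | 61% |

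In the same-type row, not all the excess is case mix. The two ratings of one patient correlate at about 0.8² = 0.64 but are counted as independent. At zero shift this already gives about 13% rejection: the critical value is in effect 1.96/√1.64 = 1.53. With random pairing the zero-shift rate is about 5%.

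**Step 3: every pair mixed.** Both groups then see the same patients, and irritability cannot confound. The independent t-test ignores the pairing, however, and becomes very conservative: about 0% rejection under the null at 90% matching with a 50/30/20 mix, against 4-5% for a paired test.

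**The case against.** The strongest reply is that the outcome is undefined, not demonstrably wrong. The Section D sentence follows directly on the PABAK-OS of intensity against irritability, so the sponsor may have had a comparison of matching in mind. If the outcome is a match score, neither mechanism applies. This stands as a condition on the point. But the Aim 3 variable is intensity, the form records intensity, and no match score is defined anywhere, so the plan has to say which is meant.

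Second, the stated Aim 3 hypothesis is addressed by PABAK-OS, which does use irritability, and the specialist comparison is supplementary. That is fair. Whether specialists choose a different intensity overall is a legitimate descriptive question, though it should not be presented as evidence on matching.

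Third, a reader might infer that the t-test can never respond to a matching difference, or that false specialist effects of up to about 60% are to be expected. The documents support neither. The first holds only with equal shares of high and low irritability. The second needs a 20-point caseload shift and same-type pairs. The documents state no caseload difference, both raters see the same patient, and Aim 3 keeps only agreed patients.

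The agreement restriction does not remove the problem: it settles each patient's irritability label but does not balance irritability between rater groups.

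**Conclusion.** The point holds conditionally. It is certain that the t-test's outcome is unnamed and that irritability does not enter it. If the outcome is chosen intensity, the test does not measure matching. It detects a large assumed difference (90% versus 40%) at about the alpha level with a balanced mix, and at about 13-19% with a 50/30/20 mix, in a form that cannot be interpreted as matching.

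Case-mix confounding is possible rather than shown. It ranges from none if all pairs are mixed, through 7-18% false rejection with random pairing, to 25-61% with same-type pairs, the last partly from counting correlated ratings as independent. All these sizes rest on assumed matching rates, caseload shifts and a proportional share of specialists. This should be changed before analysis. It does not affect Aim 1, Aim 2 or the main Aim 3 PABAK-OS.

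**What to change.** 1. State the specialist hypothesis and the outcome of the comparison, including its scoring.
2. Replace the t-test on intensity by a model of chosen intensity (ordinal, or linear on 1-3) with rated irritability, specialist status and their interaction, accounting for rater and patient. Make the interaction the specialist question.
3. If a t-test is preferred, run it on each rater's mean mismatch between the chosen level and the level the hypothesis expects for the rated irritability.
4. Analyse patients rated by one specialist and one non-specialist as a within-patient comparison, and report how many such pairs there are.
5. Tabulate irritability by specialist status so that readers can see the case mix.

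The cost is analysis-plan wording and slightly more analysis. Irritability ratings, intensity choices and certifications are already on the Appendix C forms. An interaction is harder to explain than a mean difference, and with perhaps six specialists it should be reported with its confidence interval.

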### 35 **Section B: Subjects**

#### 36 1. Number of subjects

37 Raters will be recruited from outpatient physical therapists in the St. Luke's  
38 University Health Network with an expected response of 25. Patient subjects will be  
39 recruited from a convenience sample of consecutive patients presenting for physical

therapy consultation for shoulder pain. Expected patient sample size is 90 subjects over a 6-month period. As pilot data has demonstrated  $K>0.85$  with similar methodology, this study is powered at 80% to determine a  $K>0.80$  with a sample size of 48 with a null  $K$  value of 0.40. However, due to the expected restriction of subjects in phases 2 and 3 of this study (to only those subjects with 100% agreement between raters to maintain the integrity of internal validity), doubling the required sample size is prudent to maintain power of the subsequent analyses.

## 2. Criteria for inclusion/exclusion

### *Rater Group*

**Inclusion criteria** will be state licensure as a physical therapist and regular clinical practice with patients with shoulder disorders, defined as a minimum of 500 clinical hours per year in an orthopaedic setting with >10% of patients with shoulder disorders. **Exclusion criteria** will include not meeting inclusion criteria.

### *Patient Group*

**Inclusion criteria** will be presenting with a chief complaint of shoulder pain, not extending to the neck, for outpatient physical therapy consultation. **Exclusion criteria** will include illiteracy in English and age less than 18 years. Additionally, subjects will be excluded from the study if they present with pain or symptoms distal to elbow, have had shoulder surgery on the symptomatic side in the past year, if active or passive cervical spine ROM reproduces shoulder pain, have a positive Spurling's test, or if they are unable to complete the patient reported functional questionnaires. Subjects found to have need for referral to another medical professional will be provided with the appropriate referral. If the reason for referral would prevent them from participating safely in the study, that subject will be excluded from testing.

### 3. Institutional Review Board (IRB) approval

Ethics approval has been obtained from the Institutional Review Boards of St. Luke's University Health Network (SLHN 2016-61) and Nova Southeastern University (2016-379). Written informed consent will be obtained from each subject prior to enrollment.

## Section C: Methods and Instrumentation

## **Instrumentation**

## Demographic information questionnaire

The survey will collect demographic data from raters including name, age, years of practice, advanced certification(s), gender, entry-level degree, and highest earned degree.

76        Shoulder Symptom Irritability Classification Scale

77        Raters will classify patient subjects in one of three shoulder symptom irritability  
78        levels based upon: pain level, presence of night or resting pain, onset of pain during  
79        motion, differences between active and passive range of motion, and level of disability.

80        Patient-Reported Outcome Scales

81        Three patient-rated outcome scales will be administered for the purpose of  
82        enhancing generalizability, as there is no single gold standard patient-reported outcome  
83        scale for patients with shoulder pain.

84        *Focus On Therapeutic Outcomes (FOTO)*

85        The FOTO scale is a computerized adaptive test (CAT) and will be  
86        administered via iPad (iPad 2, Apple, Cupertino, CA) at each St. Luke's Physical  
87        Therapy clinic. The FOTO scale has been found to be a reliable and valid  
88        measurement system for outpatient orthopedic rehabilitation, and has  
89        demonstrated good construct validity and responsiveness for patients with  
90        shoulder complaints. The FOTO questionnaire has a low burden on patients,  
91        with a mean test administration time of 1 minute and 29 seconds (SD = 90  
92        seconds). Furthermore, the standard error of the mean (SEM) has been found to  
93        be 1.30 with a minimal detectable change with 95% confidence (MDC95) of 3.60-  
94        10.88 functional score units. Additionally, FOTO will be utilized to collect  
95        demographic data for each patient including comorbidities, age, gender, height,  
96        weight, chronicity of symptoms, type of insurance used, level of fear avoidance,  
97        and number of surgeries.

98        *Penn Shoulder Score (PSS)*

99        The Penn Shoulder Score (PSS), originally published in 1999 and  
100        validated in 2006, is a self-report questionnaire consisting of three sections:  
101        pain, satisfaction, and function. The function subscale consists of twenty (20)  
102        items, each on a 4-point Likert scale. Each item is scored as 0 (can't do at all), 1  
103        (much difficulty), 2 (with some difficulty), or 3 (no difficulty). The item scores  
104        are then summed to determine the subscale score out of 60 (no difficulty for all  
105        items). Resultant scores for each subscale are divided by the total range from 0-  
106        100 with 0 as greatest disability and 100 as no disability. The PSS has  
107        demonstrated good test-retest reliability (ICC2,1 = 0.94) with a SEM90 of 8.5.  
108        The MDC90 is 12.1, and the minimal clinically important difference (MCID) was  
109        found to be 11.4.

110        *American Shoulder and Elbow Surgeons (ASES) Shoulder Score*

111        The American Shoulder and Elbow Surgeons (ASES) Shoulder Score,  
112        originally published in 1994 and validated in 2002, is a self-report  
113        questionnaire consisting of two sections: one visual analog scale (VAS) to

114 measure pain, and ten items to measure activities of daily living. The  
115 questionnaire takes 3 minutes to complete and is scored as follows: [(10 – VAS  
116 pain) x 5] + (5/3 x sum of ADL items). Resultant scores for each subscale range  
117 from 0-100 with 0 as greatest disability and 100 as no disability. The ASES has  
118 demonstrated good to excellent test-retest reliability (ICC = 0.61-0.96) with an  
119 SEM of 6.7. The MDC95 is 11.2, and the MCID was found to be 12.0. A  
120 recent systematic review found the ASES to be one of the only patient-reported  
121 functional scales for rotator cuff disease to have measurement error below 10% of  
122 the global score.

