#### 123 Numeric Pain Rating Scale

124 The Numeric Pain Rating Scale (NPRS) is an 11-point Likert scale that can be  
125 used to measure pain intensity. The NPRS is a standard pain assessment scale that uses a  
126 0-10 scale (no pain to worst pain imaginable, respectively) in order to determine a  
127 patient's level of pain. Patients rate their current level of pain and their worst and least  
128 amount of pain in the last 24 hours. The average of the 3 ratings is used to represent the  
129 patient's level of pain. The NPRS has demonstrated good reliability (ICC2,1=0.74) and  
130 responsiveness (MDC = 2.5, MCID = 1.1) in subjects with shoulder pain and excellent  
131 reliability in an upper extremity orthopaedic population. Furthermore, the NPRS has  
132 been used to assess pain severity of both traumatic and atraumatic etiologies.

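### Aim 2 compares function and pain across an irritability rating that is itself partly based on pain level and disability, so part of any group difference is built in

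*Combined protocol and SAP*

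**What the plan says.** Section C (Shoulder Symptom Irritability Classification Scale) has raters place patients in one of three "levels based upon: pain level, presence of night or resting pain, onset of pain during" "motion, differences between active and passive range of motion, and level of disability". That makes five criteria, two of which are pain level and disability.

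Section A, Specific Aim 2, takes this rating as the independent variable and analyses patient-reported functional "measures using analysis of variance with post-hoc analysis to compare functional disability". The hypothesis is directional: "functional status measures. The hypothesis is that patients with higher irritability will report" larger deficits. Section A names function only for this aim. Section D widens the ANOVA to differences "in patient reported functional limitation and pain subscales between shoulder symptom" irritability groups.

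Under Procedures in Section C, patients fill in the questionnaires at admission. The first therapist then rates during the examination with the help of the Appendix C intake. The second rater is blinded to the first rater's assessment, and no other blinding is described. Section E lists several limitations, but not the overlap between the rating's criteria and the Aim 2 outcomes.

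**The concern.** If the groups are formed partly on how much pain and disability a patient has, they will tend to differ on pain and disability scores whatever the other signs show. The plan states a directional hypothesis and does not describe the ANOVA as a consistency check. A small p-value would then be reported as support for the hypothesis, although part of it follows from how the groups are defined. No planned analysis looks at function across the rating's other components, so a reader could not tell the two apart.

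**Working it through.** **1. Criteria set against outcomes.** The plan states no figure for Aim 2 that could be reproduced: no effect size, SD, group split or power. The check is a comparison of texts.

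| Criterion of the rating (Section C) | Own entry on the rater sheets (Appendix C)? | Same construct among the Aim 2 outcomes? |
|---|---|---|
| Pain level | No | Yes: pain subscales; pain half of ASES |
| Night or resting pain | Yes | Partly: the PSS pain section has a rest-pain item |
| Onset of pain during motion | Yes | Not directly |
| Active versus passive motion | Yes | No |
| Disability | No | Yes: FOTO, PSS function, ASES activities |

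The two criteria that coincide with the outcomes are the two without an entry on the rater sheets. The Appendix C intake, which the first therapist uses, contains questionnaires that measure both.

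**2. Can the built-in part be sized?** No: the rating is an overall judgement without weights or cut-offs. An illustration shows how far the answer depends on assumptions. Assume five independent standard-normal criteria with equal weight, groups cut at thirds, and an outcome with correlation r to the disability criterion and none to the others. The top third of a normal variable has mean 1.091, so the high-minus-low gap is 2 × 1.091 × √(1/5) × r = 0.976r SD.

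- r = 0.3, 0.5, 0.7, 0.9 gives 0.29, 0.49, 0.68, 0.88 SD. In simulation the ANOVA rejects in about 16%, 36%, 66% and 90% of studies with 90 patients, and in about 10%, 22%, 37% and 62% with 48.
- At r = 0.7 and 90 patients, giving disability 0.25 to 2 times the weight of each other criterion moves the gap from 0.19 to 1.07 SD and rejection from 10% to 99%.
- If the groups are formed only from the three other signs, the gap is about 0 and rejection stays near 5%.

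The direction is clear. The size is not.

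**3. Precision of a comparison on the motion items.** Section C says the PSS MDC90 "is 12.1, and the minimal clinically important difference (MCID) was" 11.4, with ICC 0.94. The SEM is 12.1/(1.645 × √2) = 5.20, and the SD is 5.20/√(1 − 0.94) = 21.2 points. These are figures for the PSS as described there; using the SD and the 11.4 for the function section on a 0-100 scale is an assumption. The gap is 11.4/21.2 = 0.537 SD.

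With n = 90, equally spaced category means and critical F = 3.10 (2 and 87 df), λ = n × v × 0.537², where v is the variance of category scores 0, 0.5 and 1.

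- Equal thirds: v = 0.1667, λ = 4.32, power 43%. The 95% CI half-width for the end categories is 1.988 × √(1/30 + 1/30) = 0.51 SD, about 11 points.
- A 60/30/10 split: v = 0.1125, λ = 2.92, power 30%. Half-width 1.988 × √(1/54 + 1/9) = 0.72 SD, about 15 points.

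For the pain-adjusted version, assume motion-pain correlation 0.5 and pain-function correlation 0.6. With error-free pain, power is 52% and 38%. Of the NPRS, Section C says "The NPRS has demonstrated good reliability", with ICC 0.74. Taking 0.74 as the covariate's reliability, the residual variance is 1 − 0.36 × 0.74 = 0.734, and the score variance left after pain is 0.1667 × (1 − 0.147) = 0.142 or 0.1125 × (1 − 0.130) = 0.098. That gives λ = 5.03 and 3.46, and power 49% and 35%.

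**4. Adjusted or unadjusted?** With the same correlations, no direct motion-function link and equal thirds, the unadjusted test rejects in 63% of simulated studies; adjusted for pain, it rejects in 5% (error-free) or about 10% (reliability 0.74). If pain is a confounder, the 63% is spurious. If pain lies on the path from motion finding to function, the 63% is power for a real total effect of 2 × 1.091 × 0.5 × 0.6 = 0.65 SD, which adjustment removes. The documents do not decide between the two.

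**The case against.** The best reply is that this is ordinary known-groups validation. Aim 2 asks only whether function differs between groups, the hypothesis is one of association, and the plan never claims an effect beyond the rating's own inputs. The rating is a clinician's judgement and the outcomes come from the patient, so agreement is not guaranteed. Most of this stands, and it is why the ANOVA should remain and why only part of the difference can be called built in. It does not meet the remaining point: the plan neither labels the analysis that way nor mentions the overlap in Section E.

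Three stronger readings are tempting.

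- A reader might infer that raters assign the groups from the scored questionnaires. The documents place the intake with the first therapist and state no blinding to scores, but they do not say that scores are calculated or consulted at that moment, nor what the second rater sees.
- A reader might take the rejection rates in step 2 as the size of the bias. They rest on assumed weights and correlations.
- A reader might hold that only a pain-adjusted estimate counts. That treats pain as a confounder, which the documents do not establish.

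**Conclusion.** The concern holds as a limit on interpretation. Pain level and disability enter the rating by its own definition and return as Aim 2 outcomes, so part of any group difference is built in. A significant ANOVA shows that the rating is consistent with its criteria; it is not independent evidence that irritability relates to function or pain. That conclusion needs only the text of Sections A, C and D. The documents do not support calling the ANOVA invalid or the difference wholly an artefact, and they give no basis for a number. The power figures describe the proposed supporting comparison, not the plan. They assume 90 usable patients, an SD of about 21 points and the stated category splits.

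**What to change.** 1. In Section D, keep the ANOVA but describe it as a known-groups (consistency) check, and treat the pain-subscale comparison as descriptive. In Section E, state that pain level and disability are both rating criteria and outcomes, and that raters may use the intake scores.
2. Add one pre-specified exploratory analysis: FOTO and PSS function compared across the active-versus-passive motion item and the pain-with-motion item on the first rater's form, with mean differences and 95% CIs. Show each estimate unadjusted and adjusted for the 0-10 PSS item on today's pain, side by side. Note that pain may be a confounder or a mediator and that the pain-with-motion item is itself partly a pain measure. Do not make the adjusted estimate the only basis for conclusions.

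The cost is wording in two sections and four comparisons (two outcomes by two items), each reported two ways, from forms already in use. The downside is a more modest Aim 2 conclusion and low precision: about 30% to 50% power for an 11.4-point gap. The text should say that a non-significant exploratory result would not show absence of a relation.
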